
D2. Study Population & Eligibility Criteria

The study will be based at the ambulatory obstetrical practices of Baystate Medical Center, a large tertiary care facility in Western Massachusetts that serves a socioeconomically diverse population; 4,300 infants are delivered annually, 57% are Hispanic (predominantly from Puerto Rico with ~58% having income <\$15,000 per year). Eligible women will be Hispanic, overweight or obese (BMI >25 kg/m²), and 16-45 years of age. We will exclude women with 1) prepregnancy BMI <25 kg/m², 2) history of type 2 diabetes, heart disease, or chronic renal disease, 2) contraindications to participation in moderate physical activity or to a low-fat/high-fiber diet (e.g., Crohn's disease, ulcerative colitis), 3) inability to read English or Spanish at a 6th grade level, 4) <16 or >45 yrs of age, 5) >20 wks gestation, 6) current medications which adversely influence glucose tolerance, 7) not planning to continue to term or deliver at the study site, or 8) pregnant with twins or triplets. Women who have a very early preterm birth (<34 wks), a miscarriage, or a still birth after enrollment or a stillbirth will be excluded. Women who become pregnant again in the year following delivery will be censored at the time of their positive pregnancy test.

D3. Recruitment, Baseline Assessment, and Sample Size

Bilingual (Spanish and English) and bicultural health educators will recruit women at the first prenatal care visit (~10 wks gestation). Women will be informed of the aims/procedures of the project, sign an informed

consent, and complete a screening form to determine eligibility. The baseline assessment will be collected via standardized questionnaire and the pregnancy blood sample will be taken (see Figure 1). Expectations for the study and a contacts schedule (face-to-face meeting, mailings, booster telephone calls) will be reviewed. Each assessment and interview completed is associated with a gift card for a total of up to \$360, to be handed out after completing the study component.

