Based on observed rates in our 2 trials (R01DK074876 and ASPH/CDC S3948), we conservatively expect to 333 women over the 24 mos recruitment period. We expect 10% of women to leave the New England area, deliver elsewhere, or withdraw during pregnancy, and therefore expect 300 participants (150 in each intervention arm) at the time of delivery. We calculate that 4% of women will be excluded for very early preterm birth (<34 wks), miscarriage, or stillbirth resulting in 288 children at delivery. Over the following 1 yr, we conservatively project that an additional 8% of women will be lost to follow-up due to withdrawal or movement out of the New England area. Women who become pregnant again will be censored. Therefore, we expect 264 women and children at 1 yr postpartum.

[figure not shown]
Bilingual (Spanish and English) and bicultural health educators will recruit women at the first prenatal care visit (~10 wks gestation). Women will be informed of the aims/procedures of the project, sign an informed consent, and complete a screening form to determine eligibility.

The recruitment sites will include the Wesson Women's Clinic, Baystate Midwifery and Women's Health, Baystate Maternal-Fetal Medicine and the Baystate Perinatal Diagnostic Center. Screening is done prior to the patient's visit by a research assistant. A Centricity appointment report is reviewed which provides all women with OB appointments in the above locations. This report has the patients' name, medical record number, date of birth, ethnicity, last menstrual period, appointment reason, appointment time and location.

Based on information from the Baystate nutritionist and the Centricity roster, the research assistants will develop a potential participant list. This list will be maintained as a project on the UMASSMED REDCap server. This project will only be accessible to Baystate IRB approved staff. The pre-screened patients are then approached to determine if they are interested in participating in the study. If they are not eligible, the research assistant enters their status and/or reason for ineligibility. If women are eligible and interested, they will be informed of the aims and procedures of the project, sign an informed consent and HIPAA release, and the research assistant will initiate study procedures. If this cannot be completed in person, it will be completed over the telephone.

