Specific Aim #1, 2, 3: Impact of a Lifestyle Intervention on GWG and postpartum weight loss; biomarkers of insulin resistance; postpartum biomarkers of CVD risk. The primary analysis will evaluate differences in the change from baseline in weight gain measures, glycemia and other biomarkers of insulin resistance and cardiovascular risk factors between the groups (an intent to treat analysis). Initial analyses will describe the correlation of factors and investigate simple transformations for normality. The primary analysis will be based on a mixed model with random subject effects, including a common mean at baseline for the intervention groups, a period effect, and an intervention by period interaction.¹⁷⁰ The intervention by period interaction is a measure of the intervention effect, and corresponds to the estimate of an intervention effect in an analysis of covariance. The mixed model analysis will enable inclusion of time varying covariates such as depression, breastfeeding behaviors, and sleep, which may vary between baseline and follow-up for subjects. Equivalence of the intervention groups will be assessed by comparing the distribution of the potential confounders between each group. We will investigate established risk factors for weight gain (e.g., parity) and glycemia as well as degree and treatment for abnormality on glucose tolerance testing during pregnancy (e.g., diet, oral hypoglycemic and/or insulin) as potential confounders or effect modifiers. Generally, we will consider a change in the parameter estimate for the exposure (at least 15%), relative to that observed when not controlling for the variable as reflective of confounding. Effect modification will be evaluated by inspection of stratum specific odds ratios as well as by evaluating the statistical significance of interaction terms via likelihood ratio tests. We will also model the relationship between measured levels of exercise, sedentary behavior, and diet with each outcome, while adjusting for possible confounders using mixed effect linear regression models. We will test hypotheses with 2-sided tests. Finally, we will compare adoption and maintenance of behavior change (i.e., exercise, diet) in the intervention group relative to the control group by adding a fixed treatment group effect.

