Specific Aim #4: Evaluate the impact of a Lifestyle Intervention on the outcomes of offspring. We will evaluate the impact of intervention arm on the offspring outcomes using the methods described for Aim #1-3. We will also examine GWG and prenatal glycemic factors as predictors of glycemia and weight gain in early infancy and childhood. Important covariates are listed in the covariate section. In models focused on offspring weight gain as the outcome, we will additionally adjust for fetal growth (i.e., BW/GA z score).

Specific Aim #5: Evaluate the cost-effectiveness of the Lifestyle Intervention. We will use procedures developed in our prior studies examining the cost-effectiveness of our interventions.¹⁷¹⁻¹⁷³ We will calculate the ratio of average dollars spent per average incremental improvement in outcome (i.e., GWG, postpartum weight retention, and biomarkers of insulin resistance and CVD risk). Incremental improvement will be defined as the mean change score from baseline for each group, adjusted for baseline values of the outcome measure and other participant characteristics.

Accounting for Missing Data: Although every effort is made to avoid missing data, we plan to use propensity score techniques¹⁷⁴⁻¹⁷⁶ to evaluate the potential sensitivity of results to missing at random assumptions. Multiple comparisons will be addressed by carefully considering the biologic rationale of observed associations.

D.17. Power

To achieve power to detect clinically significant differences requires 300 participants (150 in each intervention arm) at the time of delivery. Based on observed rates in our 2 trials (R01DK074876 and

ASPH/CDC S3948), we conservatively expect 10% of women to leave the New England area, deliver elsewhere, or withdraw during pregnancy, and therefore will recruit 333 women over the 24 mos recruitment period. For offspring outcomes, we calculate that 4% will be excluded for very early preterm birth (<34 wks), miscarriage, or stillbirth resulting in 288 children at delivery. Over the following 1 yr, we conservatively project that an additional 8% of women will be lost to follow-up due to withdrawal or movement out of the New England area. Women who become pregnant again will be censored. Therefore, we expect 264 women and children at 1 yr postpartum.

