We calculated the smallest mean difference in change from baseline in the Lifestyle Intervention vs. the Health & Wellness Control arm which we could detect at 80% power using standard deviations based on our prior studies and the literature^{47, 177-180} using 2-sided tests with a significance level of alpha=5% (NCSS PASS 2008 software). For multiple regression models, we assumed that covariates accounted for 20% of the variation. Tables 3 and 4 show we have excellent power to detect even ‘small to medium’ mean differences, as defined by Cohen,¹⁸¹ ranging from ~0.30 to 0.35 SDs for a range of representative outcome measures. For example, we have 80% power to detect as small as a 2.4% difference (Table 3) in percent change in HbA1c between treatment arms. A comparable trial among Hispanics observed a 7.1% difference in percent change in HbA1c between treatment arms¹⁸² demonstrating that detecting this difference is well within the capability of the lifestyle intervention. For the categorical outcome of Compliance with IOM GWG guidelines, given our observation that 51% of overweight/obese Hispanic women exceeded guidelines in the study population, we have 80% power to detect a 30% reduction in risk or larger for exceeding IOM guidelines.

Table 3. Power Calculations Corresponding to Aim #1-3.	Projected sample size for analysis	SD for Change from Baseline	Smallest detectable mean difference in change from baseline between arms
Aim #1: GWG & Postpartum Weight Loss			
GWG (kg)	300	7.00	2.3
Postpartum weight loss	264	6.00	2.1
Physical activity (MET-hrs/wk>mod intensity)	300	2.89	0.9
Physical activity (minutes>mod intensity)	300	38.05	12.3
Total Caloric Intake (kcal/day)	300	64.90	22.4
Aim #2: Biomarkers of Insulin Resistance			
Glucose (mg/dl)	300	13.27	4.3
Insulin (pmol/l)	300	14.20	4.6
HbA _{1c}	300	0.26	0.1
HbA _{1c} (percent change)	300	7.4%	2.4%
Adiponectin (μg/ml)	300	3.40	1.1
Leptin (ng/ml)	300	5.50	1.8
HOMA	300	1.00	0.3
Aim #3: Postpartum Biomarkers of CVD Risk			
Total cholesterol (mg/dL)	264	38.38	13.3
Triglycerides (mg/dL)	264	83.06	28.7
HDL-cholesterol (mg/dL)	264	7.59	2.6
LDL-cholesterol (mg/dL)	264	33.83	11.7
Systolic blood pressure (mm Hg)	264	12.23	4.2
Diastolic blood pressure (mm Hg)	264	7.64	2.6
CRP (mg/dl)	264	4.50	1.5

Table 4. Power Calculations Corresponding to Aim #4.	Projected sample size for analysis	SD	Smallest detectable mean difference between arms
Aim #4: Offspring Outcomes at Delivery			
Cord glucose (mg/dl)	288	14	4.6

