Cord insulin (μ U/ml)	288	4.7	1.6
Cord adiponectin (μ g/ml)	288	9.7	3.2
Cord leptin (ng/ml)	288	13.6	4.5
Birthweight-for-gestational age z-score [fetal growth]	288	0.93	0.3
Birthweight (g)	288	640	212
Ponderal Index (g/cm ³)	288	0.3	0.1
Birthweight-for-length z-score (WFL-z)	288	0.77	0.3
Head circumference (cm)	288	1.1	0.4
Aim #4: Offspring Outcomes at 1yr			
Adiponectin (μ g/ml)	264	5.8	2
Leptin (ng/ml)	264	1.8	0.6
Weight-for-age z score (WFA-z)	264	0.98	0.3
Length-for-age z score (LFA-z)	264	0.94	0.3
Sum of skinfolds (mm)	264	4.2	1.5
Ratio of skinfolds	264	0.16	0.1
Waist circumference (cm)	264	2	0.7

D.18. Environment

In brief, Baystate Medical Center, the recruitment site, is the major medical resource in Western Massachusetts and the third largest acute-care hospital in New England, with 725 beds currently in service and approximately 4,500 deliveries per year. The School of Public Health and Health Sciences at UMASS maintains a micro computer research room for faculty, staff and students. Fifteen PC compatible microcomputers, a file server, a scanner and two laser printers are connected to the Department's Local Area Network (LAN). The LAN enables secure hard disk space for research projects that is accessible by multiple users and backed-up daily. [name] (Department of Laboratory Medicine, Harvard University) lab at Children's Hospital, Boston, MA is a fully equipped laboratory with all of the requisite centrifuges, water baths, pipetters, etc. required to do the hormonal assays.

D.19. Timeline

This is a 5 year study. The timeline allows 12 months for study start up and protocol development, 24 months of recruitment, and follow-up of the last remaining participant (an additional 18 months from last enrollment). Data analysis will be ongoing and the last 6 months of the study will be dedicated to final analyses and manuscript writing.

D.20. Limitations and Alternatives

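### The exclusion for birth before 34 weeks, miscarriage or stillbirth is not limited to offspring analyses; applied to mothers it conflicts with intent to treat, and it is already inside the maternal postpartum N of 264

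*Combined protocol and SAP*

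**What the plan says.** **The rule.** D2 (Study Population & Eligibility Criteria) and E.1 (Human Subjects Involvement and Characteristics) carry the same sentence: "Women who have a very early preterm birth (<34 wks), a miscarriage, or a still birth after enrollment or a stillbirth will be excluded". Neither limits it to particular outcomes. The sentence that follows in both places deals with a new pregnancy: "Women who become pregnant again in the year following delivery will be censored at the time of their positive pregnancy test".

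**Timing.** Women are recruited at about 10 weeks (D3) and randomised at about 12 weeks (D.5).

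**Analysis principle.** D.16 describes the primary analysis for Aims 1 to 3 as a comparison of change from baseline in weight measures, biomarkers of insulin resistance and "cardiovascular risk factors between the groups (an intent to treat analysis". It specifies a mixed model with a common baseline mean for the two arms. No section defines an analysis set.

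**Sample size.**
- D3 applies the exclusion to mothers: "4% of women will be excluded for very early preterm birth (<34 wks), miscarriage, or stillbirth resulting in 288 children at delivery".
- D.17 introduces it differently: "For offspring outcomes, we calculate that 4% will be excluded for very early preterm birth (<34 wks), miscarriage, or stillbirth". The same paragraph nevertheless ends: "Therefore, we expect 264 women and children at 1 yr postpartum".
- In Table 3, the column "Projected sample size for analysis" gives 300 for gestational weight gain (GWG) and every Aim 2 biomarker, and 264 for maternal postpartum weight loss and every Aim 3 outcome.
- Table 4 gives the same 264 under "Aim #4: Offspring Outcomes at 1yr".

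**The concern.** A birth before 34 weeks, a stillbirth, or a miscarriage after about 12 weeks happens after randomisation, while an intervention on weight, diet and activity is under way. If women are dropped from the maternal comparison because of such events, and the events or the women who have them differ by arm, the comparison is no longer between the groups as randomised. The common baseline mean in the D.16 model is justified by randomisation for everyone randomised. It is not automatically justified for a subset chosen afterwards. The mixed model, and the missing-data sensitivity work described with it, can use a woman's earlier measurements only if she stays in the analysis set.

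There is also a plain inconsistency. One part of the plan treats the exclusion as an offspring matter and another builds it into the maternal numbers. With no analysis set defined, an analyst could defend either choice after seeing the data.

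**Working it through.** **1. Reproduce the plan's 264.** Inputs from D3 and D.17: 300 women at delivery, 4% excluded, a further 8% lost over the year.
- Both percentages taken of 300: 300 × (1 − 0.04 − 0.08) = 264.
- Taken in sequence: 300 × 0.96 = 288; 288 × 0.92 = 264.96.
- Without the 4%: 300 × 0.92 = 276.

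The stated 264 is reached only with the exclusion in the chain. The gap is 276 − 264 = 12 women on the plan's own figure (about 11 in sequence). At delivery, 4% of 300 = 12.

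**2. Confirm that Table 3 uses these numbers.** Detectable difference = (1.960 + 0.842) × SD × √(4/N), two-sided 5%, 80% power, equal arms.
- Postpartum weight, SD 6.00, N = 264: 2.07 (stated 2.1).
- GWG, SD 7.00, N = 300: 2.26 (stated 2.3).

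So the exclusion is in the maternal postpartum row and not in the GWG row.

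**3. Effect on power.** Power = Φ(d / (SD × √(2/n)) − 1.960), n per arm.

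| Outcome | d | SD | N | n per arm | Power |
|---|---|---|---|---|---|
| Postpartum weight, exclusion applied | 2.1 | 6.00 | 264 | 132 | 81.2% |
| Postpartum weight, not applied | 2.1 | 6.00 | 276 | 138 | 82.8% |
| GWG, not applied (as Table 3) | 2.3 | 7.00 | 300 | 150 | 81.2% |
| GWG, applied (as D2 reads) | 2.3 | 7.00 | 288 | 144 | 79.6% |

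Each change is under 2 percentage points.

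**4. Possible bias (illustration only).** The documents give no event rates by arm and no figures for how excluded women differ from retained women. Assume exclusion proportions p(control) and p(lifestyle), all after randomisation, and a gap g between excluded and retained women that is the same in both arms and equals 0.5 to 1 Table 3 SD. The shift in the treatment difference is then (p(control) − p(lifestyle)) × g, in either direction.
- Equal proportions: 0.
- 3% v 5%, postpartum weight (g = 3 to 6 kg): 0.02 × g = 0.06 to 0.12 kg.
- 2% v 6%, postpartum weight: 0.04 × g = 0.12 to 0.24 kg, which is 6% to 11% of the 2.1 kg detectable difference.
- 2% v 6%, systolic pressure (SD 12.23, g = 6.1 to 12.2 mm Hg): 0.24 to 0.49 mm Hg, which is 6% to 12% of 4.2.
- GWG: 0 if Table 3's 300 is followed.

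**5. Would event counts by arm give reassurance?** With 150 per arm, Fisher's exact test at two-sided 5% has about 30% power to detect a true 2% v 6%. A non-significant difference in counts would settle little.

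**The case against.** The strongest reply is that the exclusion was meant for offspring only. D.17 introduces it that way, and Table 3 keeps 300 for GWG and all Aim 2 biomarkers. This stands in part. It confines the numerical problem to maternal postpartum weight and Aim 3, and a reader who infers that the plan drops these women from every maternal outcome goes further than the tables allow. It does not explain why D2 and E.1 are unrestricted, why D3 says women, or why Table 3's maternal postpartum rows carry 264. An offspring-only rule would not agree with those figures as they now stand.

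A second reply is that *excluded* may mean only that follow-up stops, with earlier data kept in the mixed model. A reader might infer the opposite from the next sentence, which uses *censored* for women pregnant again. The documents do not support that inference. E.1 (Sources of Materials) says that women with a positive test are removed from the study at that time, so the plan's verbs are not used distinctly and the change of word does not show that data are deleted. What stands is that the plan does not say which meaning applies.

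Third, 12 is an upper limit for events after randomisation. The rule runs from enrolment, so a miscarriage between about 10 and 12 weeks could precede randomisation, and the plan does not split the 4%. This is correct and limits the size of the point.

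E.1 also says that nobody is excluded for noncompliance. That fits an intent-to-treat aim but does not cover this rule.

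**Conclusion.** Wrong as written. An unrestricted exclusion on events that mostly follow randomisation conflicts with the stated intent-to-treat analysis wherever it is applied to mothers, and the plan contradicts itself on whether it is so applied. The exclusion is inside the projected N for maternal postpartum weight and all Aim 3 outcomes (264 against 276).

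The size is modest: at most about 12 women and under 2 points of power. A reader might conclude that the maternal results would be biased. The documents do not show that, because nothing in them says that the events, or the women who have them, differ by arm. The shifts in step 4 rest wholly on assumed splits and gaps, treat all 4% as falling after randomisation, and are zero when rates and gaps are equal. The concern is possible selection, together with an analysis set left open.

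**What to change.** 1. In D.16, define the primary maternal analysis set as all randomised women in their assigned arm.
2. In D2, D3 and E.1, limit the exclusion to offspring analyses and say what it means for data already collected.
3. Keep in the planned mixed model all maternal data already collected from these women: prenatal weights and biomarkers, delivery weight, and any postpartum data.
4. For shortened pregnancies, use the measures D.12.3 already plans: rate of gain, IOM category at the gestational age reached, and area under the weight-gain curve.
5. Report these events by arm, and use the restricted maternal set only as a sensitivity analysis.
6. Revise D3, D.17 and Table 3 to match. The maternal postpartum N lies between 264 (none of the 12 women gives postpartum data) and 276 (all are followed, with the plan's 8% loss).
7. State the postpartum N for the Aim 2 biomarkers. D.12.1 samples them in pregnancy and at 6 weeks, 6 months and 1 year postpartum, but Table 3 lists them only at 300.

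Whether follow-up continues after a loss is for the investigators to decide, and the fix does not depend on it. Retaining data already collected needs only wording; reaching 276 would mean following women whom the rule as written excludes.

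The cost is slightly more variable total GWG and some missing postpartum data. If 4% of women gain 3 to 8 kg less (assumed), the SD becomes √(49 + 0.04 × 0.96 × g²), which is 7.02 to 7.17. Power for 2.3 kg at 150 per arm then moves from 81.2% to between 80.9% and 79.3%.

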**RANDOMIZED LIFESTYLE INTERVENTION IN OVERWEIGHT AND OBESE PREGNANT
HISPANIC WOMEN**

PROTOCOL

NCT01868230

Document Date: 6-9-2014

Approach & Methods

D1. Study Overview

The overall goal of this randomized controlled trial is to test the efficacy of a culturally and linguistically modified, individually tailored lifestyle intervention to reduce excess gestational weight gain (GWG), increase postpartum weight loss, and improve maternal metabolic status among overweight/obese Hispanic women. Specific aims are to evaluate the impact of the intervention on 1) GWG and postpartum weight loss, 2) pregnancy and postpartum biomarkers of insulin resistance (i.e., glucose, insulin, HbA1c, HOMA, leptin, adiponectin), 3) postpartum biomarkers of cardiovascular risk (i.e., blood lipids, blood pressure), 4) offspring outcomes (i.e., anthropometric measures and biomarkers of insulin resistance), and 5) to evaluate the cost-effectiveness of the intervention per average incremental improvement in the outcome variables. Overweight/obese Hispanic women will be recruited in early pregnancy (around 10 wks gestation) and randomly assigned to a Lifestyle Intervention (n=150) or a Comparison Health and Wellness (control) Intervention (n=150). The intervention will utilize exercise (R01NR011295) and dietary intervention materials (R18DK067549) culturally adapted for Hispanics and shown to be efficacious in our previous controlled trials in this ethnic group. Multimodal contacts (i.e., in-person, telephone counseling, and mailed print-based materials) will be used to deliver the intervention during pregnancy (~12 wks gestation to delivery) continuing into postpartum (~6 wks to 6 mos postpartum); follow-up will continue for one year postpartum. Targets of the intervention are to achieve Institute of Medicine Guidelines for GWG and postpartum weight loss; ACOG guidelines for physical activity through increasing walking and developing a more active lifestyle; and reduction in total calories by following a balanced healthy diet in compliance with American Diabetes Association guidelines. The intervention draws from Social Cognitive Theory and the Transtheoretical Model and includes strategies for partner and/or family support to address the specific social, cultural, and economic challenges faced by underserved Hispanic women. Measures of compliance will include actigraphs and Hispanic food frequency questionnaires. The proposed project builds upon the expertise of the investigative team in conducting randomized controlled trials of exercise interventions among Hispanic pregnant women (R01 DK074876) and dietary interventions among low-income Hispanics with type 2 diabetes (R18 DK0658850) and can readily be translated into clinical practice in underserved and minority populations.

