- 2) the postpartum face-to-face meeting takes place at the routine 6 wk postpartum visit and adherence is facilitated by bus passes, cafeteria vouchers, and the 2006 Mass insurance reform law providing free health care insurance for residents earning <150% of the federal poverty level. However, if a woman does not intend to attend this visit, the health educator will meet the women at locations outside the hospital, with consideration for the participant's and the health educator or assessors level of comfort (i.e., their pediatrician's office, their home, a community center). Locations will be selected for privacy (for example, an unused exam room at a pediatrician's office) and only staff who have experience making home visits will be permitted to complete home visits.
- 3) The 6 mos and 1 yr postpartum assessments will be conducted in the hospital or at a location outside the hospital with consideration for the participant's and the health educator or assessors level of comfort
- 4) Approximately 5% of participants in our prior pregnancy cohorts left the Springfield area after delivery; however, travel funds are budgeted for assessors to travel to the broader tri-state area (MA, NY, CT) if necessary.
- 5) Delivering the intervention does not rely upon women remaining in the immediate area during the postpartum year as it is based upon tested mailed print-based materials and telephone contacts. In addition to providing home/cell/work numbers, women will be asked to provide the contact information for a person close to them. Pre-paid cell phone time will be provided as an additional incentive.

D.5. Randomization

Immediately prior to randomization (~12 weeks GA), participants will be evaluated for study inclusion by answering if their provider has restricted their physical activity during this pregnancy. If they answer yes, their medical records will be reviewed by [name] (Co-Investigator, and Director of Maternal/Fetal Medicine at Baystate). Eligible patients will be randomized into either the Lifestyle Intervention vs. the Health and Wellness Comparison Group. Randomization will be stratified based on age (<30, >30 years) and pre-pregnancy BMI (overweight >25-<30 kg/m² vs. obese >30 kg/m²). Within each strata, a blocked randomization will be used such that both treatment groups will be assigned an equal number of times in each set of 4 sequentially enrolled patients.

D.6. Intervention

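### Fixed blocks of 4 with no stated concealment leave up to one third of assignments knowable at the point of randomisation to staff who know the earlier assignments in the stratum

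*Combined protocol and SAP*

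**What the plan says.** **Sequence.** D.5 of the combined protocol and SAP says: "Randomization will be stratified based on age (<30, >30 years) and pre-pregnancy BMI", giving 2 × 2 = 4 strata. Within each, the two arms are "assigned an equal number of times in each set of 4 sequentially enrolled patients". The block size is therefore fixed and stated. D2 places the trial at one medical center, and D3 lists four recruiting locations within it. D.5 does not say who generates or holds the list, how the next assignment is concealed, or how it is released.

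**Who enrols.** D3 says "bicultural health educators will recruit women at the first prenatal care visit". It also describes research assistants who pre-screen, record ineligibility and start procedures once women "sign an informed consent and HIPAA release, and the research assistant will initiate study procedures". The account of the potential-participant list mentions several recruiters. D.14 gives recruitment, health education and telephone assessment jointly to health educators and assessors.

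**Who knows the arm.** Under D.10 the health educator sets the gestational weight-gain goal in the Lifestyle arm. D.14 blinds assessors and the record abstractor to assignment, but blinds educators only to the assessors' results. D.4 has educators explaining study requirements before randomisation.

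**The last step before assignment.** Recruitment is at about 10 weeks' gestation and randomisation at about 12. Immediately before randomisation, "participants will be evaluated for study inclusion by answering if their provider has restricted their physical activity during this pregnancy". A yes leads to record review by a co-investigator. Section E.2 describes a readiness questionnaire at the same point, again with co-investigator review and possible exclusion.

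**The concern.** In a block of known size, past assignments reveal future ones. A staff member who can work out the next arm could bring a woman's randomisation forward, delay it, or influence whether she passes the final eligibility check. Such a decision is taken before she has an arm, so the intent-to-treat analysis in D.16 cannot see or undo it. Blinded assessors protect measurement, not selection. The common-baseline mixed model and the comparison of confounders between arms help with measured imbalance but not with unmeasured differences such as motivation. The potential-participant list will yield reasons for ineligibility, but it cannot show whether a decision followed foreknowledge.

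**Working it through.** The plan gives no figure for predictability, so there is none to reproduce. Its recruitment target follows from its own inputs: 300 / 0.90 = 333.3, against 333 stated.

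**Inputs from the documents:** block of 4 with 2 per arm, four strata (D.5); 150 + 150 randomised (D1); 333 recruited over 24 months (D.17); recruitment at about 10 weeks (D3) and randomisation at about 12 (D.5).

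**1. Certainty at randomisation, all earlier assignments known.** The six possible blocks are AABB, BBAA, ABAB, ABBA, BABA and BAAB. The first two fix positions 3 and 4; the other four fix position 4 only.

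- Certain positions: 2 × 2 + 4 × 1 = 8 of 6 × 4 = 24, or 33.3%. The general formula 1/(B/2 + 1) gives 1/3 for B = 4.
- Women: 300/3 = 100, or 333/3 = 111 if every recruited woman is randomised.

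**2. Best guess.** Guess the arm used less so far in the block, and toss a coin when the arms are level. The chances of being right at positions 1 to 4 are 1/2, 2/3, 2/3 and 1. Their mean is 17/24 = 70.8%, against 50% by chance.

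**3. Partial knowledge (assumption).** Suppose the observer knows the position in the block but sees each earlier assignment with probability p. Position 3 is certain with probability p²/3 and position 4 with probability p², so the average is (p²/3 + p²)/4 = p²/3. This gives 33% at p = 1, 19% at 0.75, 8% at 0.5 and 2% at 0.25.

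**4. Certainty at consent.** Other women in the stratum may still be waiting for assignment. Assume that their number is Poisson with mean λ, that women are randomised in order of consent, and that all assignments already made are known. Then

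certain share = ¼ × (e^−λ/3 + e^−λ + λe^−λ/3).

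333 women over 24 months (about 104.4 weeks) is about 3.2 per week. With a two-week lag:

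| Stratum's share of women (assumed) | Women per week | Certain at consent |
|---|---|---|
| 10% | 0.32 | 20% |
| 25% (equal strata) | 0.80 | 9.5% |
| 40% | 1.28 | 4% |

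With equal strata, a lag of one to three weeks gives 18% to 5%.

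**5. Varied block sizes.** Simulation with 84 women per stratum and 1,500 repeats, for an observer who knows which sizes are in use but not their order, and who sees every earlier assignment:

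| Block sizes | Certain | Best guess right |
|---|---|---|
| 4 (fixed) | 33% | 71% |
| 4 and 6 | 5.6% | 69% |
| 4, 6 and 8 | 2.2% | 68% |

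Varying the sizes removes nearly all the certainty but little of the guessability.

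**The case against.** A reader might infer that recruiting educators know one third of the coming assignments. The documents do not support this, for four reasons.

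- One third is a ceiling. It needs the block size and every earlier assignment in the woman's stratum. With several recruiters and four locations, no document shows one person holding that information. D.11 does not say who makes the comparison-arm calls, so it is not stated that any one educator sees both arms.
- It applies at randomisation. The recruiting contact is about two weeks earlier, when the certain share is much lower.
- The trigger for the final check is the woman's own answer, and the record review belongs to a co-investigator. Nothing shows that this reviewer follows assignments.
- Research assistants share enrolment, so the educator's part in it is not settled.

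All four limit the size of the problem. None closes the route. Educators are still named as recruiters and meet women before randomisation. Timing is elastic, since randomisation is at about 12 weeks while D2 excludes women only beyond 20. The plan does not say that the reviewer, or whoever decides when a woman is randomised, is kept unaware of earlier assignments.

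**Conclusion.** The concern holds as a gap in safeguards. Fixed blocks of 4, no stated concealment, and recruiting staff who know the arms they deliver together leave a route to selection bias. The main openings are the timing of randomisation and the eligibility step immediately before it.

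The upper limits are one third of assignments certain (100 of 300, or 111 of 333) and a 71% best-guess rate, both for someone with full knowledge of the stratum. At consent the certain share is roughly 4% to 20%, which rests on assumed stratum shares of 40% down to 10%, a two-week lag and full knowledge of assignments already made. Incomplete knowledge lowers these figures.

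No bias in any outcome has been estimated, and nothing in the documents suggests that staff would misuse foreknowledge. The change is worth making because it is cheap and because the analysis could not repair the harm afterwards.

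**What to change.** - Release each assignment centrally, for example through the REDCap server already in use, and only after the final eligibility decision is recorded and locked. Name who generates and holds the list. This is the essential part, because varied blocks alone leave the best-guess rate at about 68%.
- Have that eligibility decision made by staff unaware of past assignments, and say so in D.5.
- Replace the fixed block with randomly varied sizes, for example 4, 6 and 8, within the same four strata, and keep the sizes out of site-facing documents.
- Reconcile D3 and D.14 on whether health educators or research assistants enrol.

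The cost is a new randomisation list, set-up of central release, and a possible within-stratum imbalance of up to 4 women (half of a block of 8) instead of 2 (half of a block of 4).
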